14.1 Sample size

Approximately 100 subjects will be randomised 1:1 to tralokinumab+TCS or placebo+TCS to facilitate an evaluation of similarity with the treatment effect observed in the LP0162-1339 trial.

Randomisation will be stratified by baseline disease severity (IGA 3 or 4).

14.2 Trial analysis sets

All screened subjects will be accounted for in the CTR.

All subjects who are randomised to treatment and exposed to IMP (tralokinumab/placebo) will be included in the full analysis set and will be analysed for efficacy up to Week 16.

A safety analysis set will be defined as all randomised subjects who receive IMP.

The decisions regarding inclusion/exclusion of subjects or subject data from the trial analysis sets will be documented in the analysis set definition document before breaking the randomisation code.

14.3 Statistical analysis

14.3.1 Disposition of subjects

The reasons for permanent discontinuation of IMP or withdrawal from trial will be presented for all randomised subjects by last visit attended and by treatment group.

14.3.2 Demographics and other baseline characteristics

Descriptive statistics of demographics and other baseline characteristics will be presented for all randomised subjects and by treatment group. Presentations of age, sex, race, ethnicity, baseline disease severity, and Worst Daily Pruritus NRS weekly average at baseline will also be given by baseline disease severity (IGA 3 or 4).

Demographics include age, sex, race, and ethnicity. Other baseline characteristics include vital signs (including height, weight, body mass index), duration of AD, concurrent diagnoses (from medical history and indications for concomitant medication), concomitant medication, and previous AD treatments.

14.3.3 Exposure and treatment compliance

The duration of exposure to treatment will be calculated as the number of days from date of first application of IMP to the date of last application of IMP, both days included.

Exposure to treatment will be presented for the safety analysis set as days of exposure per treatment group. Treatment compliance will be presented for the safety analysis set per treatment group as the percentages of missed applications/doses.

Adherence to treatment regimen will be recorded in the eCRF. If any complications or deviations in administration are observed, these will be described as protocol deviations.

14.3.4 Rescue treatment

Rescue treatment will be defined by the following algorithm:

Concomitant medications with 'Dermatitis atopic' or 'Dermatitis infected' as the preferred term (PT) for the indication, and either of the following:

- ATC2 code: H02.
- Preferred name: methotrexate, ciclosporin, azathioprine, mycophenolate-mofetil, mycophenolate-acid, mycophenolate-sodium, dupilumab, crisaborole, alitretinoin, or delgocitinib.
- ATC4 code: D07AD, D07BD, D07CD, or D07XD.
- Confirmed rescue treatment (by investigator) in reported term for the indication, and ATC4 code: D07AB, D07BB, D07CB, D07XB, D07AC, D07BC, D07CC, or D07XC.

As described in Section 9.5, investigators should make every attempt to conduct efficacy and safety assessments immediately before administering any rescue treatment. Therefore, if rescue medication has start date the same day as an efficacy assessment, then it is assumed that the assessment is not influenced by rescue treatment.

Rescue treatment will be summarised for the treatment period. In addition, a summary table of rescue treatment by type (topical and systemic) and by overall group (corticosteroids, immunosuppressants, and other) will be made for the treatment period

Additionally, rescue treatment will be summarised for the treatment period by baseline disease severity (IGA 3 or 4).

In addition, the time to first use of rescue treatment will be presented using Kaplan-Meier plots for the treatment period.

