9.5 Rescue treatment

If medically necessary (i.e. to control intolerable AD symptoms), rescue treatment for AD may be provided to the subjects at the discretion of the investigator. If possible, investigators should attempt to limit the first step of rescue treatment to topical medications (i.e. highest potency TCS) and escalate to systemic medications only for subjects who do not respond adequately after at least 14 days of topical treatment. The subjects will be monitored for signs of local or systemic TCS toxicity and the safety and appropriateness of continued use will be supervised by site staff.

Subjects who receive topical rescue treatment (highest potency TCS, JP class > Very Strong) will continue IMP treatment.

If a subject receives rescue treatment with systemic corticosteroids or non-steroidal systemic immunosuppressive drugs (methotrexate, mycophenolate mofetil, azathioprine, etc.), IMP will be immediately discontinued (see Section 10.2.2). After the treatment with these medications is completed, IMP may be resumed if deemed appropriate by the investigator, but not sooner than 5 half-lives after the last dose of systemic rescue treatment. The use of biological rescue treatment, including use of dupilumab, will be disallowed for the entire trial duration.

Investigators should make every attempt to conduct efficacy and safety assessments (at least disease severity scores [IGA and EASI], concomitant medications/procedures, and AEs) immediately before administering any rescue treatment. An unscheduled visit may be used for this purpose, if necessary.

In the primary efficacy analyses, subjects who receive highest potency TCS (JP class > Very Strong) or systemic rescue treatment during the treatment period will be considered as non-responders.

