9.7 Prohibited medications and procedures

The medications and procedures listed below are prohibited during the trial from randomisation (Week 0). Medications and procedures disallowed prior to randomisation are

covered by the exclusion criteria (see Section 8.3). In case any prohibited treatments are used during the trial, they must be recorded in the eCRF as concomitant medication.

From randomisation through end of treatment (Week 16):

- PDE-4 inhibitors.
- TCS of highest potency (JP class > Very Strong).
- Topical JAK inhibitors.
- Use of UVA or UVB, psoralen+UVA (PUVA), other phototherapy, or tanning beds.
- 3 or more bleach baths per week.

From randomisation through safety follow-up (Week 20):

- Investigational agents other than tralokinumab.
- Systemic corticosteroids (nasal, ophthalmic and inhaled corticosteroids are allowed).
- Systemic treatment with an immunosuppressive/immunomodulating agent (examples include: cyclosporine A, mycophenolate mofetil, azathioprine, methotrexate, JAK inhibitors, interferon-gamma, dupilumab, or other biologics).
- Allergen immunotherapy.
- Live (attenuated) vaccine.
- Immunoglobulins.
- Blood products.

Some of the above mentioned prohibited medications can be used during the treatment period (Week 0 to Week 16) provided the indication is rescue treatment for AD. Please refer to Section 9.5 for details regarding rescue treatment.

The sponsor's medical expert will determine whether IMP discontinuation is required.

Please note that receipt of inactive/killed vaccines (e.g. inactive influenza) is allowed, provided they are not administered within 5 days before/after any trial visit.

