10.2.2 Reasons for temporary discontinuation of IMP

IMP administration may be temporarily suspended in the event of:

- Other intercurrent illnesses or major surgery.
- An infection that requires parental treatment with antibiotic, antifungal, antiviral, anti-parasitic, or anti-protozoal agents.

IMP administration should be temporarily suspended in the event of:

- Treatment with systemic corticosteroids or non-steroidal immunosuppressive/immunomodulating medications (e.g. cyclosporine, methotrexate, azathioprine, mycophenolate mofetil, JAK inhibitors, dupilumab or other biologics).

After the treatment with any of the medications mentioned in this section, IMP may be resumed if deemed appropriate by the investigator, but not sooner than 5 half-lives after the last dose of systemic therapy.

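### Section 9.5 makes any systemic rescue a non-response, but the 14.3.4 algorithm that identifies rescue does not code AD-indicated systemic JAK inhibitors, biologics other than dupilumab, or other unlisted systemic immunosuppressants.

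*Protocol*

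**What the plan says.** Protocol 14.3.4 takes concomitant medications coded to atopic or infected dermatitis "as the preferred term (PT) for the indication, and either of the following". Four conditions follow:

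- ATC2 code H02.
- One of ten preferred names. They include methotrexate, ciclosporin and azathioprine, and end with "mycophenolate-sodium, dupilumab, crisaborole, alitretinoin, or delgocitinib".
- Topical steroid codes D07AD, D07BD, D07CD or D07XD.
- Investigator-confirmed rescue, but only together with a further set of D07 codes.

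The section also plans "a summary table of rescue treatment by type (topical and systemic) and by overall group (corticosteroids, immunosuppressants, and other) will be made".

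Protocol 9.5 states the analysis consequence without reference to a drug list: subjects given topical steroid of the highest class "or systemic rescue treatment during the treatment period will be considered as non-responders". It also says: "The use of biological rescue treatment, including use of dupilumab, will be disallowed for the entire trial duration".

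Protocol 9.7 prohibits systemic immunosuppressive or immunomodulating treatment by class, with examples that include "JAK inhibitors, interferon-gamma, dupilumab, or other biologics". It accepts that some prohibited medications may be given as AD rescue. Protocol 10.2.2 foresees use of these drugs: "IMP administration should be temporarily suspended in the event of" treatment with systemic steroids or non-steroidal agents, the examples ending in "mycophenolate mofetil, JAK inhibitors, dupilumab or other biologics".

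SAP 6.5 sets the time window of the rescue table and replaces the Kaplan-Meier plot. SAP 6.8.7 refers back to the protocol for intercurrent events. Neither changes the algorithm.

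**The concern.** Rescue medication is the intercurrent event that turns an observed Week 16 response into a non-response in the primary composite analysis (14.3.6.1). The protocol describes that event in two ways, and the version that can be programmed is narrower than the stated rule. The list is not simply confined to permitted rescue, because it contains dupilumab, which 9.5 disallows as rescue. Nothing explains why one disallowed biologic is coded and the others are not.

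If 14.3.4 is followed, an IGA 0/1 or EASI75 response after an unlisted systemic drug is credited to randomised treatment, against the reasoning in 14.3.6.1. For SCORAD and DLQI, the observed value replaces worst observation carried forward (14.3.7.1). Later data also stay in the hypothetical repeated-measures analysis unless IMP is permanently discontinued (14.3.7.2). There is no formal testing (14.3.5), so what is at stake is the estimate and confidence interval used to judge similarity with LP0162-1339.

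**Working it through.** **Step 1. Run each AD-indicated therapy through both rules.**

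| Therapy given for AD | Coded as rescue by 14.3.4? | Non-response under 9.5? |
|---|---|---|
| Systemic corticosteroid | Yes (H02) | Yes |
| Methotrexate, ciclosporin, azathioprine, mycophenolate | Yes (by name) | Yes |
| Dupilumab | Yes (by name) | Yes, as a systemic drug, though disallowed as rescue |
| Highest-potency topical steroid | Yes (D07 conditions) | Yes |
| Systemic JAK inhibitor | No, unless delgocitinib, which is matched by name and not by route | Yes |
| Biologic other than dupilumab | No | Yes, as a systemic drug, though disallowed as rescue |
| Other unlisted systemic immunosuppressant | No | Yes |

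Investigator confirmation cannot close the gap, because it counts only alongside a D07 code.

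**Step 2. Look for another rule that would catch these subjects.** The 14.3.6.1 sensitivity analysis sets permanent IMP discontinuers to non-response, but 10.2.2 calls only for temporary suspension. SAP 6.8.2 dates permanent discontinuation only where a reason for it is recorded. Major deviations are summarised and listed (SAP 6.8.9) with no effect on response. The blinded review in 14.2 and 14.3.16 states no rule for these drugs.

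**Step 3. Size for a binary endpoint.** The plan gives no figure to reproduce here. About 100 subjects are randomised 1:1 (14.1), so about 50 per arm.

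- One reclassified responder: 1/50 = 2.0 points in that arm and in the difference.
- Expected shift = (users in one arm minus users in the other) × P(user counts as responder) × 2.0. With an assumed probability of 0.25 to 0.75, one user gives 0.5 to 1.5 points, three users split 2:1 give the same, and three users in one arm give 1.5 to 4.5.
- Unstratified 95% half-width = 1.96 × √[p₁(1−p₁)/50 + p₀(1−p₀)/50]. For assumed rates of 30% v 10% it is 15.2 points; 40 v 20, 17.5; 50 v 30, 18.8; 60 v 40, 19.2; 80 v 60, 17.5.
- One user relative to the half-width: 0.5/19.2 = 2.6% to 1.5/15.2 = 9.9%.

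Illustration with assumed rates of 50% v 30%: the difference is 20.0 points (1.2 to 38.8). One uncaptured responder on placebo makes it 18.0 (−1.0 to 37.0); one on tralokinumab makes it 22.0 (3.2 to 40.8). An interval that crosses zero carries no decision in this trial.

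**Step 4. Size for SCORAD.** Replacing an assumed improvement of 20 to 50 points by no change, in one subject, moves the arm mean by 20/50 = 0.4 to 50/50 = 1.0 point. The half-width is 1.96 × SD × √(2/50), which is 5.9 for an assumed SD of 15 and 7.8 for 20. The shift is therefore 0.4/7.8 = 5% to 1.0/5.9 = 17% of a half-width.

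Steps 3 and 4 treat each user as otherwise uncaptured, so they are upper-end illustrations.

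**The case against.** The strongest counter-argument is that few subjects can reach the gap. Section 9.5 asks investigators, where possible, to start rescue with highest-potency topical steroid and to move to systemic drugs only after an inadequate response to at least 14 days of it. A subject who follows that ladder should already be coded as rescued through the D07 conditions. This stands. What remains is the subject who skips the topical step, which the wording allows, or who receives a biologic despite the ban.

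It can also be said that 9.5 already makes these subjects non-responders, so the protocol gives the right answer. This stands in part: it makes the problem an inconsistency between two sections and not a settled wrong rule. But 14.3.4 is what would be programmed, and SAP section 4 says only that the analysis follows the protocol, without saying which section governs.

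A change to the primary definition may also weaken comparability with LP0162-1339, whose algorithm is not in these documents. That is a fair cost, and a supplementary analysis meets it.

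A reader might infer that phototherapy for AD is a missed rescue event too, since 9.7 prohibits it and a response after it is equally hard to credit to randomised treatment. The documents do not support this. Sections 6 and 14.3.6 name two intercurrent events, rescue medication and permanent discontinuation of IMP. Section 9.5 describes rescue as topical and then systemic drugs, and 9.7 permits only some prohibited medications as rescue. Counting phototherapy would widen the event, which is a choice and not a correction.

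**Conclusion.** The point holds for systemic drugs. AD-indicated systemic JAK inhibitors other than delgocitinib, biologics other than dupilumab, and other unlisted systemic immunosuppressants are non-response events under 9.5 but are not coded as rescue by 14.3.4, and no other stated rule reliably catches them. A reader might go further and infer that the primary result is materially biased, or biased towards tralokinumab. The documents do not support that. They give no frequency of use, the topical-first ladder removes many candidates, and direction depends on the arm: uncaptured responders on tralokinumab inflate the difference, while those on placebo shrink it and make the present rule conservative for tralokinumab.

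The firm figure is 2 points per reclassified responder, given 50 per arm. The 3 to 10% of a half-width for one user rests on assumed response rates and an assumed chance that the user counts as a responder. The SCORAD range rests on assumed changes and SDs. The impact is likely small. The reason to act is that the primary endpoint's intercurrent event should have one definition before the blind is broken.

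**What to change.** Before unblinding, extend 14.3.4 through SAP 6.5. Count as rescue any AD-indicated systemic immunosuppressive or immunomodulating drug, identified by class or ATC code and including JAK inhibitors and all biologics. It must have started after first dose and before the Week 16 visit, or before Day 112 if that visit did not take place. Keep the existing rule for rescue starting on the day of an assessment. Apply the existing handling: non-response for binary composite endpoints, worst observation carried forward for continuous ones, and exclusion of later data under the hypothetical estimand. Treatment policy is unchanged. Tabulate the added drugs as systemic. Drugs given for other indications stay outside.

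Report the primary endpoints under the present 14.3.4 algorithm as a supplementary analysis, for comparison with LP0162-1339. If wanted, a further optional supplementary analysis can treat AD-indicated phototherapy as non-response; it should not enter the primary analysis.

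The cost is a few lines of SAP text and one supplementary run, since concomitant medications are already collected. A few subjects may become non-responders, and the primary definition may differ from that of LP0162-1339.

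### The rescue algorithm in Protocol 14.3.4 recognises non-steroidal systemic drugs only by a closed name list, so a subject given an unlisted one for AD could count as a responder, although 9.5 makes any systemic rescue a non-response

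*Protocol*

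**What the plan says.** Protocol 9.5 sets the non-response rule that the main analysis is meant to follow: "subjects who receive highest potency TCS (JP class > Very Strong) or systemic rescue treatment during the treatment period will be considered as non-responders". It describes the non-steroidal part of systemic rescue as an open class: "non-steroidal systemic immunosuppressive drugs (methotrexate, mycophenolate mofetil, azathioprine, etc".

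Protocol 14.3.4 turns rescue into an algorithm. A concomitant medication counts if its indication codes to Dermatitis atopic or Dermatitis infected and it meets one of four conditions:

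- ATC2 code H02.
- One of ten names: "Preferred name: methotrexate, ciclosporin, azathioprine, mycophenolate-mofetil, mycophenolate-acid, mycophenolate-sodium, dupilumab, crisaborole, alitretinoin, or delgocitinib".
- One of four D07 codes (D07AD, BD, CD, XD).
- "Confirmed rescue treatment (by investigator) in reported term for the indication, and ATC4 code: D07AB", or one of seven further D07 codes.

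Other sections foresee systemic drugs beyond these names. Protocol 9.7 lists systemic immunosuppressive or immunomodulating agents that are prohibited ("examples include: cyclosporine A, mycophenolate mofetil, azathioprine, methotrexate, JAK inhibitors, interferon-gamma, dupilumab, or other biologics"), then says that some prohibited medications may be given as AD rescue and refers back to 9.5. Protocol 8.3 (criterion 7) and 10.2.2 also name JAK inhibitors as systemic drugs of this kind.

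SAP 6.5 changes the rescue plot and sets the time window for the rescue table. SAP 6.8.7 leaves intercurrent events to the protocol. Neither alters the definition.

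**The concern.** The primary estimand is response achieved without rescue medication. If the programmed definition is narrower than the rule it implements, a subject whom 9.5 calls a non-responder can enter the primary analysis as a responder. The same flag also governs EASI90 and EASI50, worst observation carried forward for SCORAD and DLQI, and data exclusion in the hypothetical-estimand models. With no formal testing (14.3.5), the estimates and intervals carry the comparison with LP0162-1339, so the definition behind them should match the stated rule.

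**Working it through.** **Step 1: can the algorithm see an unlisted non-steroidal systemic drug?** I read H02 as systemic corticosteroids, D07 as topical corticosteroids, and delgocitinib as the only JAK inhibitor among the ten names. The protocol does not spell these out.

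| Route in 14.3.4 | Flags an unlisted non-steroidal systemic drug? |
|---|---|
| H02 | No, corticosteroids only |
| Ten preferred names | No, closed list without a class term |
| D07AD, BD, CD, XD | No, topical codes |
| Investigator-confirmed rescue plus another D07 code | No, confirmation alone is not enough |

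No route corresponds to the open end of the class in 9.5. Every drug that 9.5 names is covered.

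**Step 2: follow such a subject to Week 16.** The subject receives a systemic JAK inhibitor coded to an AD indication, has no earlier flagged rescue, and meets EASI75 at Week 16.

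- IMP suspended (9.5, 10.2.2): no flag, so the observed Week 16 value is used and the subject is a responder. The 14.3.6.1 sensitivity analysis gives the same result.
- IMP permanently stopped: the primary analysis in 14.3.6.1 keeps retrieved Week 16 data, so the subject is still a responder. Only the sensitivity analysis makes this subject a non-responder.

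**Step 3: which results depend on the flag?**

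| Endpoint | Planned treatment difference that uses the flag | Planned treatment difference that does not |
|---|---|---|
| IGA 0/1, EASI75, pruritus NRS reduction ≥4 | Composite | Treatment policy (14.3.6.2, 14.3.7) |
| EASI90, EASI50 | Composite (14.3.8) | None |
| SCORAD, DLQI | Composite, by worst observation carried forward (14.3.7.1); hypothetical (14.3.7.2) | None |

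The hypothetical models also drop data after permanent discontinuation. There the gap matters when IMP is only suspended.

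**Step 4: size.** The plan states no figure on this point to reproduce. Protocol 14.1 gives about 100 subjects randomised 1:1, so about 50 per arm.

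*Shift per subject.* In stratum s the Mantel-Haenszel difference moves by w_s/n_arm,s, where w_s = [n1s·n0s/(n1s+n0s)] divided by its sum over strata.

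- Balanced strata (IGA 3/4 splits per arm of 15/35, 25/25, 30/20 or 35/15): 1/50 = 2.0 points.
- Mild imbalance (27 vs 23 in IGA 3, 23 vs 27 in IGA 4): each stratum term is 27×23/50 = 12.42, so each weight is 0.5. The shift is 0.5/27 = 1.85 or 0.5/23 = 2.17 points.

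*Net shift.* For k subjects with b on placebo, the shift is 2(k−b) − 2b points. One subject gives +2 or −2; two give +4, 0 or −4. The range of 0 to 2 subjects is assumed.

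*Against the interval.* I use the unstratified half-width 1.96·√[p0(1−p0)/50 + p1(1−p1)/50], with assumed control rates of 10–50% and differences of 10–25 points.

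- Smallest (10% vs 20%): 1.96·√(0.25/50) = 13.9 points.
- Largest (40% vs 50%, or 50% vs 60%): 1.96·√(0.49/50) = 19.4 points.
- One subject is 2/19.4 = 10% to 2/13.9 = 14% of the half-width. Two in the same arm are 4/19.4 = 21% to 4/13.9 = 29%.

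*Continuous endpoints.* Assume the carried-forward worst value exceeds the observed Week 16 value by 20–50 SCORAD points or 5–20 DLQI points. One subject then moves an arm mean by 20/50 = 0.4 to 50/50 = 1.0, or by 5/50 = 0.1 to 20/50 = 0.4.

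**The case against.** **The conflict is thin.** The drugs 9.5 names are all captured. The conflict rests on the open end of its list and on an inference from 9.7 that JAK inhibitors may be given as rescue. This stands as a limit: no section states that permission. But 9.5 covers systemic rescue without restricting it to the named drugs. The algorithm also does not depend on permission. Protocol 9.5 says "The use of biological rescue treatment, including use of dupilumab, will be disallowed for the entire trial duration", yet dupilumab is on the list.

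**A reader might infer that three of the eight systemic examples in 9.7 are permitted rescue drugs that go unflagged.** The documents do not support that. Section 9.7 is a list of prohibited drugs. Biologics other than dupilumab are disallowed as rescue, so they matter only through disallowed use. Interferon-gamma appears only as prohibited. The realistic gap is systemic JAK inhibitors and other unnamed non-biologic immunosuppressants.

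**A reader might also infer that SCORAD and DLQI have no analysis free of the flag.** That goes too far. Section 14.3.10 plans DLQI summaries by visit, and 14.3.16 sets observed cases for by-visit tabulations. What is missing is a treatment-difference estimate.

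**Safeguards exist.**

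- Investigators should "escalate to systemic medications only for subjects who do not respond adequately after at least 14 days of topical treatment", so many such subjects would be flagged earlier. The step applies only where possible.
- The sensitivity analysis covers permanent discontinuation, but after systemic rescue "IMP may be resumed if deemed appropriate by the investigator", no sooner than five half-lives after the last dose.
- The medical expert's decision on IMP (9.7), the blinded reviews (14.2, 14.3.16), the concomitant-medication table (SAP 6.1) and the listing of major deviations (SAP 6.8.9) make unlisted use visible. None of them changes the flag.

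**A closed list is reproducible.** That is a real merit. The fix keeps it by ending in fixed names.

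**Conclusion.** The point holds at low-to-moderate severity. The algorithm is narrower than the rule in 9.5, and the SAP does not repair it. A misclassified subject needs an unlisted systemic drug with an AD indication before Week 16, no earlier flagged rescue and an observed Week 16 response. It does not matter for the primary analysis whether IMP was suspended or stopped.

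Each such subject is worth about 2 points on a primary endpoint, or 10–14% of the interval half-width under the assumed response rates. The documents give no rate of such use; the count may be zero.

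Nothing supports reading this as bias toward tralokinumab. Cases on placebo shift the difference the other way, and one case in each arm cancels when strata are balanced. The treatment-policy analyses of IGA 0/1, EASI75 and pruritus NRS are unaffected.

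**What to change.** Keep every entry in 14.3.4: H02, all ten names and the D07 rules. Add to SAP 6.5:

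*Also counted as rescue: (a) any other systemic immunosuppressive or immunomodulating drug, including JAK inhibitors and biologics, whose indication has the preferred term Dermatitis atopic or Dermatitis infected; (b) any systemic drug that the investigator confirmed as rescue for AD.*

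Fix the resulting preferred names at the blinded review already planned in 14.3.16, and record them before the code is broken.

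The cost is a few lines of text and one check of concomitant medications. Protocol 9.6 already collects these with indication and dates, so no new data are needed. The downside is that a few more subjects may become non-responders. If no such drug was used, no result changes.
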